4.3 Description of Study Procedures

4.3.1 Efficacy

4.3.1.1 Lower Respiratory Tract Infection

Subjects will be monitored throughout the study for LRTI (see [Table 5](#) and [Table 6](#)). All subjects seeking medical attention for a respiratory illness (in either the inpatient or outpatient setting) will be evaluated for LRTI. All subjects found to have an LRTI and all subjects who require hospitalization for a respiratory infection, even if there is not a diagnosis of LRTI, should have respiratory samples obtained and respiratory assessment forms completed. Samples should be collected for all of these respiratory events even those not meeting the protocol definition of LRTI. Subjects who have a primary hospitalization for a respiratory infection (ie, upper or lower tract) or a respiratory deterioration during a hospitalization, or who seek outpatient medical attention (including ER visits) for a lower respiratory illness, will be assessed clinically for the presence of LRTI and for RSV by central laboratory diagnostic testing of respiratory secretions. Testing for RSV will be performed using the US FDA-cleared and CE-marked in vitro diagnostic real-time RT-PCR assay (Lyra RSV + human metapneumovirus [hMPV] assay; Quidel Corporation, San Diego, CA, www.quidel.com; see [Section 4.3.1.2](#)). A diagnosis of RSV LRTI requires having a respiratory sample positive for RSV by the central laboratory RT-PCR assay.

In addition to the clinical assessment of LRTI, there is a protocol definition using objective criteria for the determination of a medically attended protocol-defined LRTI.

For subjects with no underlying lung disease:

To meet the protocol-defined endpoint of medically attended RSV LRTI, subjects with signs of LRTI must have documented at least one physical examination finding of rhonchi, rales, crackles, or wheeze AND at least one of the following clinical signs (see [Table 7](#)):

- Increased respiratory rate at rest (age: < 2 months, ≥ 60 breaths/min; 2 to 6 months, ≥ 50 breaths/min; > 6 months, ≥ 40 breaths/min), OR
- Hypoxemia (in room air: oxygen saturation < 95% at altitudes $\leq 1,800$ meters or < 92% at altitudes > 1,800 meters), OR
- Clinical signs of severe respiratory disease (eg, acute hypoxic or ventilatory failure, new onset apnea, nasal flaring, intercostal, subcostal or supraclavicular retractions, grunting) or dehydration secondary to inadequate oral intake due to respiratory distress (need for intravenous fluid).

Table 7 Criteria for Meeting the Protocol-defined Endpoint of Medically Attended RSV LRTI - Subjects Without Underlying Lung Disease

RSV	Lower Respiratory Tract	Medical Significance
RSV Confirmed: 
 Positive by central laboratory real-time RT-PCR assay 	Documented physical examination findings localizing to lower respiratory tract: 
 Rhonchi Rales Crackles Wheeze 	Objective measures of clinical severity: 
 Increased respiratory rate Hypoxemia Acute hypoxic or ventilatory failure New onset apnea Nasal flaring Retractions Grunting Dehydration due to respiratory distress

LRTI = lower respiratory tract infection; RSV = respiratory syncytial virus; RT-PCR = reverse transcriptase-polymerase chain reaction.

Note: One item from each column is required to meet the protocol-defined endpoint of medically attended RSV LRTI.

For subjects with underlying lung disease (CLD or CHD):

To meet the protocol-defined endpoint of medically attended RSV LRTI, subjects with signs of LRTI must have documented at least one new or worsened physical examination finding of rhonchi, rales, crackles, or wheeze AND at least one of the following clinical signs (see [Table 8](#)):

- Increase in baseline respiratory rate by $\geq 20\%$ at rest and that rate is greater than the age-based criteria established for children with no underlying lung disease (age: < 2 months, ≥ 60 breaths/min; 2 to 6 months, ≥ 50 breaths/min; > 6 months, ≥ 40 breaths/min), OR
- Hypoxemia (O_2 saturation $< 95\%$ in room air or O_2 saturation drop of 5 percentage points from baseline in children with baseline O_2 saturation $< 95\%$ in room air, or acute documented need for supplemental O_2 or increased O_2 requirement compared with baseline), OR
- Clinical signs of severe respiratory disease (eg, acute hypoxic or ventilatory failure, new onset apnea, nasal flaring, intercostal, subcostal or supraclavicular retractions, grunting) or dehydration secondary to inadequate oral intake due to respiratory distress (need for intravenous fluid), OR
- Prescription of new or increased (from baseline) dose of medications including bronchodilators, steroids, diuretics, cardiac medications

Table 8 Criteria for Meeting the Protocol-defined Endpoint of Medically Attended RSV LRTI – Subjects With Underlying Lung Disease (CLD or CHD)

RSV	Lower Respiratory Tract	Medical Significance

RSV Confirmed:
 
 Positive by central laboratory real-time RT-PCR assay 	
Documented new or worsened physical examination findings localizing to lower respiratory tract:
 
 Rhonchi Rales Crackles Wheeze 	
Objective measures of clinical severity:
 
 Increased respiratory rate (from baseline) Hypoxemia Acute hypoxic or ventilatory failure New onset apnea Nasal flaring Retractions Grunting Dehydration due to respiratory distress Prescription of new or increased (from baseline) dose of medications including bronchodilators, steroids, diuretics, cardiac medication

CHD = congenital heart disease; CLD = chronic lung disease; LRTI = lower respiratory tract infection; PE = physical examination; RSV = respiratory syncytial virus; RT-PCR = reverse transcriptase-polymerase chain reaction.

Note: One item from each column is required to meet the protocol-defined endpoint of medically attended RSV LRTI.

RSV Hospitalization

An RSV hospitalization is defined as either (1) a respiratory hospitalization with a positive RSV test within approximately 2 days of hospital admission (primary) or (2) a new onset of respiratory symptoms in an already hospitalized subject, with an objective measure of worsening respiratory status and positive RSV test (nosocomial). Primary and nosocomial RSV hospitalization are further defined below.

Primary RSV Hospitalization

RSV diagnostic testing will be performed on respiratory secretions obtained within approximately 2 days before or after admission for subjects hospitalized for any respiratory infection (upper or lower respiratory tract). If the RSV diagnostic test (performed centrally via RT-PCR) is positive, the hospitalization will be classified as a primary RSV hospitalization. Deaths that can be demonstrated as caused by RSV (by autopsy or clinical history and virologic evidence) will also be considered as primary RSV hospitalization endpoints.

Nosocomial RSV Hospitalization

Subjects hospitalized for a respiratory illness or non-respiratory illness whose RSV diagnostic test is negative may develop nosocomial RSV illness during the study.

If signs (such as retractions, rhonchi, wheezing, crackles or rales) of a new lower respiratory illness occur during a hospitalization, whatever the reason for hospitalization, and there is an objective measure of worsening respiratory status (that is, new requirement for supplemental oxygen, increase in supplemental oxygen requirement from prior to the onset of symptoms, or need for new or additional mechanical ventilation), a specimen will be collected within approximately 2 days from worsening of respiratory status for RSV diagnostic testing by the central laboratory. For any subject who is hospitalized for a respiratory infection (upper or lower respiratory tract), the subject must return to his/her baseline respiratory status or be clearly resolving the preceding respiratory illness before a subsequent respiratory deterioration for a nosocomial RSV hospitalization event can be determined.

If the RSV diagnostic test (performed centrally via RT-PCR) is positive, the subsequent hospital days will count as a nosocomial RSV hospitalization. The days of RSV hospitalization will be counted beginning with the start of the respiratory deterioration that resulted in the RSV diagnostic test.

RSV LRTI Outpatient Events

Subjects who seek outpatient medical attention, including ER and urgent care visits, for an LRTI should have respiratory secretions obtained within approximately 2 days after the initial healthcare provider assessment.

4.3.1.2 Respiratory Secretions for RSV Detection

Respiratory secretions for RSV testing must be collected from all subjects with LRTIs (inpatient or outpatient) and from all hospitalized subjects with any new respiratory infection (upper or lower) within approximately 2 days after the initial healthcare provider assessment and diagnosis. Nasal secretions will be obtained unless the subject is intubated, and then tracheal secretions may be obtained.

Respiratory secretions will be tested in a central laboratory for RSV using the US FDA-cleared and CE-marked in vitro diagnostic real-time RT-PCR assay (Lyra RSV + hMPV assay; Quidel Corporation, San Diego, CA, www.quidel.com). Testing may include other respiratory pathogens.

4.3.1.3 Monitoring for RSV Resistance

As an exploratory endpoint, novel RSV F variants identified in RSV-positive nasal specimens (based on the RSV diagnostic test results; Section 4.3.1.2) from all subjects will be evaluated

by genotypic and phenotypic methods to monitor potential susceptibility changes to MEDI8897 and palivizumab neutralization. The subtype and genotypic determination of RSV will be performed directly on the nasal specimens that are collected from all subjects who are confirmed RSV-positive using the Lyra RSV + hMPV real-time RT-PCR assay manufactured by Quidel Corporation (Lyra RSV + hMPV assay; Quidel Corporation, San Diego CA, www.quidel.com). The full-length F gene will be amplified using a standard, single-tube population-based RT-PCR method and sequenced by Sanger sequencing methodology. Amino acid substitution(s) within the MEDI8897 binding site (amino acid [aa] 62-69 and aa 196-212) and outside the binding site in the extracellular regions of mature F protein (aa 24-109 and aa 137-524) will be reported and compared to F protein sequences of contemporary reference RSV strains. In vitro phenotypic analysis (susceptibility to MEDI8897 and palivizumab neutralization) will be attempted using an RSV neutralization assay with either RSV viruses constructed through site-directed mutagenesis of the F gene and reverse genetics or by cloning the F gene from the isolate into a laboratory-adapted RSV strain such as A2 or B9320.

4.3.2 Medical History and Physical Examination, Weight, and Vital Signs

A complete medical history will be obtained at screening and a medical history update will be obtained during the treatment and follow-up period as defined in Section 4.2. Assessment will include history and current medical conditions, past or present cardiovascular disorders, respiratory, gastrointestinal, renal, hepatic, neurological, endocrine, lymphatic, hematologic, immunologic, dermatological, genitourinary, drug and surgical history, or any other diseases or disorders.

A physical examination, including weight, will be performed at screening and during the treatment and follow-up period as defined in Section 4.2.

Vital signs (temperature, blood pressure, heart rate, and respiratory rate) will be collected at screening and during the treatment and follow-up period as defined in Section 4.2. On days when study drug is administered, vital signs will be obtained within 60 minutes prior to dosing, and at 30 minutes (± 5 minutes) and 60 minutes (± 5 minutes) post dose.

Baseline information will be collected on breastfeeding, smoking in the household, and if the infant attends day care.

4.3.3 Pharmacokinetic Evaluation and Methods

A Laboratory Manual will be provided to the sites that specifies the procedures for collection, processing, storage, and shipment of samples, as well as laboratory contact information, specific to this clinical research study.

Blood samples will be collected to evaluate PK of MEDI8897 and palivizumab in serum (see Section 4.2.2 for collection time points). Subjects in the CLD/CHD cohort requiring a

replacement dose of study drug due to cardiac surgery with cardiopulmonary bypass will have a blood sample collected before and after surgery (prior to administering replacement dose) to evaluate serum concentration of MEDI8897 or palivizumab. The PK of MEDI8897 and palivizumab will be measured utilizing validated assays.

4.3.4 Anti-drug Antibody Evaluation and Methods

Blood samples will be collected to evaluate ADA responses to MEDI8897 and palivizumab in serum (see Section 4.2.2 for collection time points). Evaluation will be performed using validated immunoassays. Tiered analyses will be performed to include screening, confirmatory, and titer assay components, and the positive-negative cut points will be statistically determined from drug-naive validation samples. Samples will be utilized for further characterization of the ADA response, including ADA to the YTE domain on MEDI8897 and the assessment of neutralizing antibody to MEDI8897 or palivizumab.

4.3.5 RSV-neutralizing Antibody and RSV Serology Evaluations and Methods

4.3.5.1 RSV Neutralizing Antibody

Blood samples will be collected to evaluate anti-RSV neutralizing antibody levels in serum (see Section 4.2.2 for collection time points). Analyses will be performed using an RSV neutralizing antibody assay previously described by Shambaugh et al ([Shambaugh et al, 2017](#)).

4.3.5.2 RSV Serology

Blood samples will be collected to measure RSV antigen-specific antibody levels in serum (see Section 4.2.2 for collection time points). Evaluations will be performed using a validated immunoassay similar to the assay described by Maifeld et al ([Maifeld et al, 2016](#)).

4.3.6 Healthcare Resource Utilization and Caregiver Burden

Information on HRU and caregiver burden will be collected for all events of medically attended LRTI (see [Table 5](#) and [Table 6](#)). This will include admission to and duration of hospital and intensive care unit (ICU) stay, number of subjects who require respiratory support and supplemental oxygen use, duration of respiratory support and supplemental oxygen use, number and type of outpatient visits (eg, ER, urgent care, outpatient clinic), and the number of prescription and over-the-counter (OTC) medications and their duration of use. Caregiver burden will be assessed through, for example, caregiver missed work days and the subject's absence from day care.

4.3.7 Skin Reactions

Skin reaction assessment will be done for any post-dosing skin or skin-related reaction to assist in determination of the etiology of the reaction (see [Table 5](#) and [Table 6](#)). Information

will be collected regardless of event severity, duration, time of onset post dosing, or relationship to investigational product. Parents/legal representatives of study subjects will be given a hypersensitivity card and instructed to call the study site immediately for signs of hypersensitivity or allergic reaction. Sites must notify MedImmune within 24 hours of knowledge of such events. For any skin or skin-related reactions, including all rashes that occur within 7 days after dosing, the child will be brought to the study site as soon as possible for evaluation.

4.3.8 Estimate of Volume of Blood to be Collected

Blood volume estimates are provided by visit/study day for Season 1 ([Table 9](#)) and Season 2 ([Table 10](#)).

Table 9 Volume of Blood to be Collected, Season 1

Visit/Study Day	Estimated Blood Volume (mL)
Visit 1/Screening or Visit 2/Day 1	1.5 mL
Visit 4 /Day 31	1.5 mL
Visit 8/Day 151	1.5 mL
Visit 9/Day 361	1.5 mL
Total	6.0 mL

Table 10 Volume of Blood to be Collected, Season 2

Visit/Study Day	Estimated Blood Volume (mL)
Visit 12/Day 31	1.5 mL
Visit 16/Day 151	1.5 mL
Visit 17/Day 361	1.5 mL
Total	4.5 mL

4.4 Study or Study Component Suspension or Termination

MedImmune reserves the right to temporarily suspend or permanently terminate this study or component of the study at any time. The reasons for temporarily suspending or permanently terminating the study may include but are not limited to the following:

- 1 Death in any subject in which the cause of death is assessed as related to investigational product (in this case the study will be paused for the sponsor safety review committee to evaluate the events)
- 2 Anaphylactic reaction that is related to investigational product (see [Appendix B](#) for a definition of anaphylaxis; in this case the study will be paused for the sponsor safety review committee to evaluate the events)

- 3 Grade 3 and/or 4 hypersensitivity AEs based on the National Cancer Institute Common Terminology Criteria for Adverse Events (NCI CTCAE) grading scale that are assessed as related to MEDI8897 in 2 or more subjects
- 4 Two SAEs of the same type that are assessed as related to MEDI8897
- 5 Other events that, in the judgment of the sponsor or site investigator, are deemed serious enough to warrant immediate review by the sponsor safety review committee
- 6 Subject enrollment is unsatisfactory
- 7 Sponsor decision to terminate development

If MedImmune determines that temporary suspension or permanent termination of the study or component of the study is required, MedImmune will discuss the reasons for taking such action with all participating investigators (or head of the medical institution, where applicable). When feasible, MedImmune will provide advanced notice to all participating investigators (or head of the medical institution, where applicable) of the impending action.

If the study or component of the study is suspended or terminated for safety reasons, MedImmune will promptly inform all investigators, heads of the medical institutions (where applicable), and/or institutions conducting the study. MedImmune will also promptly inform the relevant regulatory authorities of the suspension/termination along with the reasons for such action. Where required by applicable regulations, the investigator or head of the medical institution must inform the Institutional Review Board (IRB)/Independent Ethics Committee (IEC) promptly and provide the reason(s) for the suspension/termination. If the study or component of the study is suspended for safety reasons and it is deemed appropriate by MedImmune to resume the study or component of the study, approval from the relevant regulatory authorities (and IRBs/IECs when applicable) will be obtained prior to resuming the study.

4.5 Investigational Products

4.5.1 Identity of Investigational Products

MedImmune will provide the investigators with MEDI8897 and palivizumab (Table 11) using designated distribution centers.

Table 11 Identification of Investigational Products

Investigational Product	Manufacturer	Concentration and Formulation as Supplied
MEDI8897	MedImmune	Supplied as 50 mg (nominal) per vial solution. The solution contains 100 mg/mL MEDI8897. [REDACTED] The nominal fill volume is 0.5 mL.
Placebo	Various (sourced by sites)	Commercially available 0.9% (w/v) saline (sterile for human use)

Table 11 Identification of Investigational Products

Investigational Product	Manufacturer	Concentration and Formulation as Supplied
Palivizumab	AstraZeneca	Supplied as 50 mg (nominal) per vial solution. The solution contains 100 mg/mL palivizumab, 25 mM Histidine, 1.6 mM glycine, 12.5 mM chloride, pH 6.0. The nominal fill volume is 0.5 mL.

HCl = hydrochloride; w/v = weight/volume.

MEDI8897 and palivizumab will be supplied to the site in open-labeled kits. Each kit has a unique number printed on all labels within the kit (ie, the outer carton label and the label of each vial).

4.5.1.1 Investigational Product Inspection

Each vial selected for dose administration should be inspected. Refer to [Table 11](#) for identification of investigational product.

If there are any defects noted with the investigational product, the investigator and site monitor should be notified immediately. Refer to the Product Complaint section (Section [4.5.1.4](#)) for further instructions.

4.5.1.2 Dose Preparation Steps and Treatment Administration

The first day of dosing is considered Day 1.

Study drug (MEDI8897, placebo, and palivizumab) will be supplied by an unblinded investigational product manager. Blinding will be performed at the site level to ensure that MEDI8897, placebo, and palivizumab are indistinguishable in appearance and are not labeled to reveal treatment identity.

No incompatibilities between MEDI8897 or palivizumab and polycarbonate or polypropylene syringes have been observed.

MEDI8897 and palivizumab do not contain preservatives and any unused portion must be discarded. Total in-use storage time from needle puncture of the study drug vial to administration should not exceed 4 hours at room temperature. If storage time exceeds these limits, a new vial should be used.

MEDI8897 group: Season 1 and Season 2, including replacement dose(s) after cardiopulmonary bypass

Subjects will receive MEDI8897 for Dose 1 and placebo for Doses 2 through 5:

1 Season 1

(a) Infants < 5 kg body weight at time of dosing:

- Dose 1: A dose of 50 mg (ie, 0.5 mL) MEDI8897 will be obtained by withdrawing the entire contents of 1 investigational vial with an appropriately sized syringe, and administered as one single (ie, 0.5 mL) injection
- Doses 2 through 5: A corresponding volume (0.5 mL) of saline will be obtained, and administered as one single (ie, 0.5 mL) injection

(b) Infants ≥ 5 kg body weight at time of dosing:

- Dose 1: A dose of 100 mg (ie, 1.0 mL) MEDI8897 will be obtained by withdrawing the entire contents of 2 investigational vials
- Doses 2 through 5: A corresponding volume (1.0 mL) of saline will be administered
- To maintain the blind:
 - If the weight is ≥ 5 kg to < 6.7 kg then the dose should be administered as one single (ie, 1.0 mL) injection
 - If the weight is ≥ 6.7 kg, then the volume of MEDI8897 or saline should be divided equally into 2 syringes

2 Season 2

- Dose 1: A dose of 200 mg (ie, 2.0 mL) MEDI8897 will be obtained by withdrawing the entire contents of 4 investigational vials
- Doses 2 through 5: A corresponding volume (2.0 mL) of saline will be administered
- To maintain the blind:
 - If the weight is < 13.4 kg, then the dose should be administered as two 1.0 mL injections (ie, 1.0 mL per injection)
 - If the weight is ≥ 13.4 kg, then the volume of MEDI8897 or saline should be divided equally into 3 syringes

3 Replacement dose(s) after cardiopulmonary bypass

Season 1

(a) Cardiopulmonary bypass < 90 days post first dose of MEDI8897 (or most recent replacement dose if previous cardiopulmonary bypass) for infants < 5 kg:

- Replacement dose: A dose of 50 mg (ie, 0.5 mL) MEDI8897 will be obtained by withdrawing the entire contents of 1 investigational vial with an appropriately sized syringe, and administered as one single (ie, 0.5 mL) injection

- (b) Cardiopulmonary bypass < 90 days post first dose of MEDI8897 (or most recent replacement dose if previous cardiopulmonary bypass) for infants ≥ 5 kg:
 - Replacement dose: A dose of 100 mg (ie, 1.0 mL) MEDI8897 will be obtained by withdrawing the entire contents of 2 investigational vials
 - To maintain the blind:
 - If the weight is ≥ 5 kg to < 6.7 kg then the dose should be administered as one single (ie, 1.0 mL) injection
 - If the weight is ≥ 6.7 kg, then the volume of MEDI8897 should be divided equally into 2 syringes
- (c) Cardiopulmonary bypass ≥ 90 days post first dose (or most recent replacement dose if previous cardiopulmonary bypass) for all weights:
 - Replacement dose: A dose of 50 mg (ie, 0.5 mL) MEDI8897 will be obtained by withdrawing the entire contents of 1 investigational vial with an appropriately sized syringe, and administered as one single (ie, 0.5 mL) injection

Season 2

- (a) Cardiopulmonary bypass < 90 days post first dose:
 - Replacement dose: A dose of 200 mg (ie, 2.0 mL) MEDI8897 will be obtained by withdrawing the entire contents of 4 investigational vials
 - To maintain the blind:
 - If the weight is < 13.4 kg, then the dose should be administered as two 1.0 mL injections (ie, 1.0 mL per injection)
 - If the weight is ≥ 13.4 kg, then the volume of MEDI8897 should be divided equally into 3 syringes
 - (b) Cardiopulmonary bypass ≥ 90 days post first dose (or most recent replacement dose if previous cardiopulmonary bypass):
 - Replacement dose: A dose of 100 mg (ie, 1.0 mL) MEDI8897 will be obtained by withdrawing the entire contents of 2 investigational vials
 - To maintain the blind:
 - If the weight is ≥ 5 kg to < 6.7 kg then the dose should be administered as one single (ie, 1.0 mL) injection
 - If the weight is ≥ 6.7 kg, then the volume of MEDI8897 should be divided equally into 2 syringes
- 4 Switch the needle prior to administration
 - 5 MEDI8897 or placebo (saline) should be administered in the anterolateral aspect of the thigh according to standard practice procedures for IM injections. The injection should be given using standard aseptic technique. When possible, injection sites for subsequent injections should use alternating sites (eg, right then left thigh). The maximum volume to be administered with each injection is 1.0 mL
 - 6 MEDI8897 or placebo (saline) should be administered using the appropriate size needle ranging from 22 to 25 gauge and 5/8 to 1.0 inches based on muscle size and weight of the subject

Palivizumab group: Season 1 and Season 2, including replacement dose(s) after cardiopulmonary bypass

- 1 A dose of 15 mg/kg palivizumab will be obtained by withdrawing the calculated volume of drug to the nearest 0.01 mL as described below:

The dose of palivizumab will be calculated based on the subject's weight (to the nearest 0.01 kg) using the following formula:

$$\text{Dose (mL)} = [\text{subject weight (kg)} \times \text{dose level (15 mg/kg)}] \div \text{palivizumab concentration (100 mg/mL)}$$

The corresponding volume of palivizumab should be rounded to the nearest 0.01 mL.

Examples:

A patient who weighs 4.90 kg at the time of injection receives 0.74 mL of study drug (4.90 kg x 15 mg/kg) ÷ 100 mg/mL = 0.735 mL (rounded to 0.74 mL)

A patient who weighs 3.70 kg at the time of injection receives 0.56 mL of study drug (3.70 kg x 15 mg/kg) ÷ 100 mg/mL = 0.555 mL (rounded to 0.56 mL)

- 2 Switch the needle prior to administration
- 3 Palivizumab should be administered in the anterolateral aspect of the thigh according to standard practice procedures for IM injections. The injection should be given using standard aseptic technique. When possible, injection sites for subsequent injections should use alternating sites (eg, right then left thigh). The maximum volume to be administered with each injection is 1 mL
- 4 Palivizumab should be administered using the appropriate size needle ranging from 22 to 25 gauge and 5/8 to 1.0 inches based on muscle size and weight of the subject

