3.1.2.3 Season 1 or Season 2, CLD/CHD Cohort - Replacement Dose

Subjects in the CLD/CHD cohort who undergo cardiac surgery with cardiopulmonary bypass after receipt of Dose 1 but prior to receipt of Dose 5 will receive a replacement dose of the study drug that they received for Dose 1 immediately following the surgery when determined by the physician to be medically stable for an IM injection. Any subsequent doses of study drug will continue to be given according to the protocol-specified dosing schedule. In subjects requiring multiple surgeries during the same season, the dosing and timing scheme described below should be followed relative to the most recent replacement dose.

Details for the replacement dose by randomized group are presented below.

MEDI8897 Group

- Season 1
 - Subjects undergoing surgery < 90 days post first dose who originally received 50 mg MEDI8897 will receive a single 50-mg MEDI8897 IM replacement dose if < 5 kg body weight at time of replacement dosing or a single 100-mg MEDI8897 IM replacement dose if \geq 5 kg body weight at time of replacement dosing.
 - Subjects undergoing surgery < 90 days post first dose who originally received 100 mg MEDI8897 will receive a single 100-mg MEDI8897 IM replacement dose.
 - Subjects undergoing surgery \geq 90 days post first dose who originally received either 50 mg or 100 mg MEDI8897 will receive a single 50-mg MEDI8897 IM replacement dose.
- Season 2
 - Subjects undergoing surgery < 90 days post first dose will receive a single 200-mg MEDI8897 IM replacement dose.
 - Subjects undergoing surgery \geq 90 days post first dose will receive a single 100-mg MEDI8897 IM replacement dose.

Palivizumab Group

Subjects will receive a 15 mg/kg palivizumab IM replacement dose. Thereafter, doses should be given according to the protocol-specified dosing schedule.

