3.2 Rationale for Dose, Population, and Endpoints

3.2.1 Dose Rationale

A single fixed 50-mg IM dose was shown to be efficacious in the Phase 2b Study D5290C00003 in preterm infants (29 to < 35 weeks GA) in their first RSV season. Model-based analyses of the Phase 2b clinical PK and efficacy data identified a projected serum $AUC_{0-\infty}$ of [REDACTED] as the protective exposure threshold. The risk of medically attended RSV-confirmed LRTI over the course of the RSV season was significantly lower in infants with higher projected $AUC_{0-\infty}$. Infants with $AUC_{0-\infty}$ above [REDACTED] had a statistically significantly higher probability of protection based on exposure-response analysis using Cox proportional hazard regression. [REDACTED]

[REDACTED] Henceforth, based on these analyses, a stratified fixed dosing strategy by weight bands will be implemented to ensure an adequate dose to maintain MEDI8897 serum concentrations above the target AUC

throughout the RSV season. Based on dose optimization analysis designed to maximize the proportion of infants with clinically efficacious MEDI8897 serum exposure, a single fixed 50-mg IM dose will be administered for infants < 5 kg in their first RSV season while a single fixed 100-mg dose will be administered for those weighing \geq 5 kg entering their first RSV season. Additionally, the body weight range for the Phase 2/3 population in the second year of life at time of dosing is expected to be approximately 8.5 to 15 kg. Therefore, with the same rationale, a single fixed 200-mg dose of MEDI8897 is proposed for infants in the second year of life to achieve and maintain efficacious exposure during the entire second RSV season.

The approved palivizumab dosing regimen of 15 mg/kg administered IM once monthly during the RSV season (ie, once monthly for 5 months) will be used for this study.

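### Protocol 4.5.1.2 departs from 3.1.2.3 on the MEDI8897 replacement dose: a missing clock in one Season 2 row and a weight conflict in Season 1

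*Protocol*

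**What the plan says.** Two sections of the Protocol set the replacement dose for MEDI8897 recipients who have cardiac surgery with bypass between Dose 1 and Dose 5.

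**Section 3.1.2.3** gives the rule by season.
- Season 2: 200 mg if surgery is under 90 days after the first dose, 100 mg at 90 days or later.
- Season 1, under 90 days: infants first given 50 mg are dosed by their weight at replacement (50 mg below 5 kg, 100 mg from 5 kg). Infants "who originally received 100 mg MEDI8897 will receive a single 100-mg MEDI8897 IM replacement dose", with no weight condition.
- Season 1, 90 days or later: 50 mg for all.
- Several surgeries in one season: "the dosing and timing scheme described below should be followed relative to the most recent replacement dose". This covers both seasons.

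**Section 4.5.1.2** repeats the rule as preparation steps, in five MEDI8897 rows.
- Season 1 (a), 50 mg: "Cardiopulmonary bypass < 90 days post first dose of MEDI8897 (or most recent replacement dose if previous cardiopulmonary bypass) for infants < 5 kg"
- Season 1 (b), 100 mg: "Cardiopulmonary bypass < 90 days post first dose of MEDI8897 (or most recent replacement dose if previous cardiopulmonary bypass) for infants ≥ 5 kg"
- Season 1 (c), 50 mg: "Cardiopulmonary bypass ≥ 90 days post first dose (or most recent replacement dose if previous cardiopulmonary bypass) for all weights"
- Season 2 (a), 200 mg: "Cardiopulmonary bypass < 90 days post first dose"
- Season 2 (b), 100 mg: "Cardiopulmonary bypass ≥ 90 days post first dose (or most recent replacement dose if previous cardiopulmonary bypass"

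Five places send the reader to 3.1.2.3 for replacement dosing: 3.1.1, 3.1.2.1, 3.1.2.2, Table 5 footnote h and Table 6 footnote g. Section 4.5.1.2 does not, and no text says which section prevails.

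**The concern.** Section 4.5.1.2 is the step from which the syringe is prepared, and its MEDI8897 heading says that it covers replacement doses. It departs from 3.1.2.3 in two ways, which differ in kind.

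1. **Season 2, an omission.** Row (a) is the only one of the five rows that does not restart the clock after an earlier replacement. For some second operations the preparer finds no matching row, or reads row (b) literally and prepares half the dose that 3.1.2.3 gives.
2. **Season 1, a conflict.** Section 3.1.2.3 lets the original 100-mg dose decide, whereas 4.5.1.2 lets weight decide. For an infant first given 100 mg who now weighs under 5 kg, the two give different doses.

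What is at stake is a single clear dose for an infant after bypass. In the Season 1 case there is also a classification problem: SAP 3.4.4 counts a wrong dose of study drug as an important deviation, and the documents do not settle which of the two doses would be wrong. That problem does not arise in Season 2, where 3.1.2.3 supplies the answer.

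**Working it through.** The plan states no figure to reproduce here. The check applies both sections to the same situations.

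**Season 2, second bypass**

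Inputs: the 90-day threshold (both sections); Dose 5 on Day 121 ± 2 days (Table 6); replacement only before Dose 5 (3.1.2.3). Let *r* be the days from Dose 1 to the first replacement and *t* the days from Dose 1 to the second bypass. Dose 5 on Day 121 is 120 days after Dose 1, so *t* ≤ 119.

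Example with *r* = 40 and *t* = 100:
- 3.1.2.3: 100 − 40 = 60 < 90, so 200 mg.
- 4.5.1.2 row (a): 100 ≥ 90, so it does not apply.
- 4.5.1.2 row (b), clock at the latest replacement: 60 < 90, so it does not apply. If the parenthetical is read as a plain alternative, 100 ≥ 90 satisfies the row and it gives 100 mg.

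In general the gap needs *t* ≥ 90, *t* > *r*, *t* − *r* < 90 and *t* ≤ 119. The number of affected days is

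min(119, *r* + 89) − max(90, *r* + 1) + 1

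| *r* | Affected *t* | Days |
|---|---|---|
| 1 | 90 | 1 |
| 10 | 90–99 | 10 |
| 20 | 90–109 | 20 |
| 30 to 89 | 90–119 | 30 |
| 90 | 91–119 | 29 |
| 100 | 101–119 | 19 |
| 118 | 119 | 1 |

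With Dose 5 on Day 119 the last *t* is 117, and the maximum is 117 − 90 + 1 = 28 days. With Dose 5 on Day 123 the last *t* is 121, and the maximum is 121 − 90 + 1 = 32 days.

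Outside the gap the sections agree: *t* < 90 gives 200 mg in both, and *t* − *r* ≥ 90 gives 100 mg in both.

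**Season 1, first bypass**

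Weight is taken at the replacement dose.

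| Days since Dose 1 | Original dose | Weight now | 3.1.2.3 | 4.5.1.2 |
|---|---|---|---|---|
| < 90 | 50 mg | < 5 kg | 50 mg | 50 mg |
| < 90 | 50 mg | ≥ 5 kg | 100 mg | 100 mg |
| < 90 | 100 mg | < 5 kg | **100 mg** | **50 mg** |
| < 90 | 100 mg | ≥ 5 kg | 100 mg | 100 mg |
| ≥ 90 | 50 mg | < 5 kg | 50 mg | 50 mg |
| ≥ 90 | 50 mg | ≥ 5 kg | 50 mg | 50 mg |
| ≥ 90 | 100 mg | < 5 kg | 50 mg | 50 mg |
| ≥ 90 | 100 mg | ≥ 5 kg | 50 mg | 50 mg |

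One of the 8 combinations conflicts. The documents do not show that 100 mg is the right answer. The dose rationale in 3.2.1 says that "a single fixed 50-mg IM dose will be administered for infants < 5 kg in their first RSV season", which favours 50 mg.

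**The case against.** The Season 2 point is already answered elsewhere. The repeat-surgery sentence in 3.1.2.3 covers both seasons, and row (b), directly below row (a), restarts the clock, so a careful reader reaches 200 mg. This stands, and it is why the point is a gap in the preparation step and not a contradiction. The step still does not carry the rule itself.

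The Season 1 conflict depends on row (a) meaning weight at replacement, which the row does not say. That reading is the natural one: the Dose 1 rows of 4.5.1.2 and the 50-mg bullet of 3.1.2.3 both use weight at dosing. It remains an assumption.

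The five pointers could be taken to make 3.1.2.3 the controlling section. They say where the details are, but none says that 3.1.2.3 overrides 4.5.1.2.

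The 28 to 32 day maximum holds only if Dose 5 is given within its visit window. Eligibility for a replacement ends when Dose 5 is received, so a late or missed Dose 5 would lengthen the gap. This stands.

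Finally, both situations should be uncommon, and no sample size or planned analysis depends on them. This also stands, and it limits the severity.

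**Conclusion.** Both departures are in the current Protocol text, and the concern holds as a minor inconsistency between two operative dosing sections.

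- **Season 2:** an omission that 3.1.2.3 resolves. It affects a second bypass at least 90 days after Dose 1 but under 90 days after the latest replacement, a window of at most 30 days with Dose 5 on Day 121. The possible error is 100 mg in place of 200 mg, or no dose identified.
- **Season 1:** a true conflict of 100 mg against 50 mg in 1 of 8 first-surgery combinations, with no rule of precedence.

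The conclusion assumes that weight means weight at replacement and, for the size of the window, that Dose 5 is on schedule. Rarity is an inference, since the documents give no counts. The first case needs two bypass operations before Dose 5 in one Season 2. The second needs an infant dosed at 5 kg or more to weigh under 5 kg within 90 days. Pooled summaries would barely change.

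**What to change.** **Season 2.** Add to row (a) of 4.5.1.2 the parenthetical on the most recent replacement dose that the other four rows carry. Every repeat bypass then falls in exactly one row and matches 3.1.2.3. The example above gives 200 mg in both sections.

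**Season 1.** The sponsor should choose one rule and state it in both sections.
- *Option A, current weight decides.* Change the 100-mg bullet in 3.1.2.3 so that infants under 5 kg at replacement get 50 mg. This fits the weight bands in 3.2.1.
- *Option B, original dose decides.* Limit Season 1 row (a) of 4.5.1.2 to infants first given 50 mg, and extend row (b) to all infants first given 100 mg. Row (b) then needs an injection line for infants under 5 kg, because its present lines start at 5 kg. One 1.0 mL injection is within the section's volume limit.

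The cost is wording only: one parenthetical for Season 2, and for Season 1 either one bullet (A) or two row labels and one injection line (B). A clarification letter or the next amendment would do.
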